Hypothesis 1.1: Bladder instillation with a gentamicin antimicrobial solution will result in significantly decreased episodes of symptomatic UTIs, fewer courses of oral antibiotics, and a reduction of multi-drug resistant organisms on urine culture, as compared to controls.

Hypothesis 1.2: Bladder instillation with a gentamicin antimicrobial solution will decrease detrusor spasms, increase bladder compliance as well as mitigate the rapid rise in systolic blood pressure (autonomic dysreflexia) evidenced during cystometry as compared to controls.

B. Study Design/Methodology

In a randomized, double-blind, prospective study, we will compare the long-term effects (80 daily sessions, 2x per day) of a bladder instillation protocol in 3 groups of individuals (n=36; 3 groups of 12) with chronic SCI receiving either:

1) gentamicin bladder instillation

2) saline installation

3) no instillation (catheter clamping only in those with suprapubic catheters for the duration of the irrigation time frame - refer to Fig. 2 timeline).

The control groups will also serve to address the question of whether bacteria already colonized in the bladder would also provide a protective role in preventing more pathogenic bacteria or other organisms, such as yeast, which also colonize the bladder. Research participants will complete the 80 sessions of twice per day instillations initially in the Urogenital and Bowel Laboratory, where blood pressure and heart rate will be continually monitored (approximately 1-2 weeks). Once safe pressures are established, the remaining instillations may be completed in the home setting. A major issue confounding validity of a clinical trial is compliance. Given that this study assesses the long-term outcomes of daily bladder instillations and allows for the twice-daily instillations to be conducted in the home-setting, it is possible that participants may not be fully

compliant with respect to study duration and frequency of instillations. In an effort to improve the applicability of the study results to individual participants and mitigate non-compliance, our research nurse will guide participants through all aspects of the instillation procedure to ensure that they are fully independent. At-home blood pressure monitoring during instillation times is automatically recorded and will be an additional step in monitoring protocol adherence.

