sessions will be performed in the laboratory. The time frame to retain the instillation treatment in the bladder will be incrementally increased by 15 minute intervals in the laboratory over the course of 3 - 4 weeks. Instillation retention times may begin for 30 minutes. Once 3 consecutive days of stable blood pressure values without autonomic dysreflexia are demonstrated during that time frame, the time will be increased to 45 minutes and the same process will continue by 15 minute intervals, up to 2 hours, as long as blood pressure remains stable throughout the instillation retention time frame. The instillation retention time frame will not be increased if the participant experiences autonomic dysreflexia and thus, an optimal time frame in which his/her blood pressure remains stable during the intervention will be established. Once 3 consecutive stable days are achieved with the same instillation parameters and the participant has demonstrated self-sufficient use of the instillation procedure, he/she will be sent home for one day to perform the twice daily instillations at home. For home instillations, the participant will be instructed and provided with written instructions indicating that the solution is to be stored in the refrigerator no more than 10 days and stored at room temperature for no more than 48 hours. The participant will return to the laboratory the following day for instillation with blood pressure monitoring. Provided blood pressure parameters remain stable, the participant will be allowed to complete the intervention at home for 3 days prior to returning to the laboratory for instillation and blood pressure monitoring. If blood pressure parameters remain stable, the participant will be able to begin the home intervention program of 6 days a week and 1 day in the lab. Participants will be instructed to monitor blood pressure for at least 15 minutes.

2. Saline Instillation

A 50ml syringe containing saline will be connected to the end of the catheter and slowly infused over 1-2 minutes after drainage of urine is complete. The saline will remain in the participant's bladder for at least 30 minutes (unless the participant is experiencing autonomic dysreflexia, and in that case, immediately drained) with the goal of attaining 2 hours. Note that participants will follow the same instillation training paradigm as mentioned above, including the incremental progression of instillation retention time with stable blood pressure values.

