3. Bladder Clamping Protocol – no instillation (for those with suprapubic catheters)

Participants with suprapubic catheters will be instructed by the research urology nurse on how to perform a catheter clamping protocol. These procedures will initially be conducted in the laboratory setting until the participant can demonstrate independence with clamping and blood pressure remains stable during that time frame. To begin, the nurse will instruct the participant on how to slide the plastic piece of the suprapubic tube to the "closed" position and plug the end of the tube. This will ensure that urine is not draining from the tube. After the tube has been clamped for 15 minutes, the participant will un-clamp the suprapubic tube, take the plug off the end, and draining any additional urine into a collecting "hat" or urinal. What comes out of the suprapubic tube will be measured. The nurse will record this amount on a chart as a measurement of the participant's bladder capacity. This procedure will be repeated 4 times a day until he/she can work up to clamping for 30 minutes, increased by 15 minute intervals, up to 2 hours as indicated above in the instillation description (if appropriate). Each day the nurse will help the participant re-clamp the tube, plug the end, and continue recording residual urine that comes out of the tube. At night, the participant may keep the suprapubic tube connected to a bag in order to let the bladder drain during sleep. When the participant is able to demonstrate independence with clamping, he/she will restart bladder clamping in the home setting, clamping the suprapubic catheter 4 times a day for up to 2 hours each time. He/she will continue to clamp the suprapubic tube throughout the duration of this study.

4. Urine Sample Collection and Culture

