Urine collected for cultures will be collected as a clean-catch midstream technique from an immediately installed urine catheter or as a suprapubic aspiration from an installed catheter (52). For participants having a suprapubic catheter, the catheter will be clamped for 20 to 30 minutes until at least 5 mL of urine can be collected. The catheter will then be unclamped, and urine will be allowed to flow into a sterile plastic container. In those that use intermittent catheterization, participants will be required to first cleanse the urethral area with a castile soap towelette. A sterile 12 French straight catheter is inserted through the urethra into the bladder. The first portion of the urine stream should flow into the toilet in order to reduce the opportunities for contaminants to enter into the urine stream. The urine midstream is then collected into a clean container (any excess urine will be emptied into the toilet), Urine samples will be placed in

sterile storage vials and stored at 4C for less than 3 hours and sent to the Outpatient Care Center, Jewish Hospital for analysis. Symptomatic UTIs will be defined as a participant complaint of symptoms consistent with UTI (cloudy/foul smelling urine, fever, chills, increase in bladder and/or lower extremity spasms, worsening dysreflexia, leakage, or pain) combined with a positive leucocyte esterase and/or nitrates on dipstick urinalysis or a urine microscopy with > 10 WBC/HPF (white blood cells/high powered field) with a urine culture with >10⁵ bacteria/ml (46). Note that urine smell and cloudiness alone (i.e. without other symptoms) are not considered UTI signs, given their high prevalence in this catheterizing population. All cultured microorganisms will be identified to the species level and quantified as colony-forming units per ml (cfu/ml⁻¹) (16). If the microorganism(s) cultured is/are resistant to three or more different antimicrobial agents to which the microorganism would normally be susceptible, it will be defined as being multi-resistant. If a participant is diagnosed having a symptomatic UTI necessitating systemic antibiotics by the study physician/nurse practitioner, he/she will follow standard of care treatment under provider oversight. The study physician/nurse practitioner will recommend whether or not continuation of either the instillation or clamping protocol is appropriate for the participant during systemic antibiotic treatment.

5. Blood Draw

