A medical event is defined within our program as any untoward or unfavorable medical occurrence in a human research participant that occurs during the enrollment period of a study. All medical events for study participants will be recorded in a log for tracking and reporting, as the team is made aware of them. Medical events that occur during a research visit will be reported to the study nurse and then elevated to the study physician if not immediately resolved. The physician will evaluate these medical events, to determine causality with relation to the research and referral for medical care. A weekly report of all medical events is generated by the research nurse and sent to the study physician (and physician assistant), the principal investigator, the regulatory core, and the study physical therapists for review of causality and follow-up. We have developed a table outlining the most common expected events in our SCI population. These events occur with this population on a daily basis. This table will allow the IRB and our staff to understand how expected and unrelated events will be documented and reported. If a physician outside the study team treats the medical event, the study physician will follow the event to assess the following:

- The medical condition affecting their medical eligibility for research
- Determination on causality of the event
- The event's effect on research assessments or training paradigms

All conclusions reached by the study physician will be reported to the PI. If another physician treats the medical issue the study physician will follow the individual to only assess whether the medical condition affects their medical eligibility in the study or any of the research assessments or training paradigms and will notify the principal investigator. These non-study related medical events are followed by the research team and will be reported to the IRB as outlined in Medical Reporting Table. A weekly report of all medical events is generated by the research nurse and sent to the study physician (and physician assistant), the principal investigator, and the study physical therapists. In this study, a medical event will only be reported if it occurs on the same day that the assessment associated with this study also occurs.

5. Data Safety and Monitoring Plan

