Day-to-day oversight of the trial is provided by the Principal Investigators (PIs), Drs. [name] and [name]. They will review all study data and any adverse events, and report all adverse events to the Medical Monitor, sponsor, and University of Louisville IRB. Monitoring for the study will be provided by a Medical Monitor who will review study conduct including accrual, drop-outs, protocol deviations, and AEs in aggregate on an annual basis. The Medical Monitor will review serious adverse events (SAEs) in real-time. All data analyses (Labs, urodynamics, ultrasound) will be conducted as assessed with annual summary reports generated. Study data will be provided to the Medical Monitor to each annual review

one month prior. Data reports will be prepared by the principal investigators and the study statistician. The Medical Monitor will provide a written report to the study team with recommendations for study modification, study continuation/discontinuation as relevant. The study team is responsible for forwarding the report to the IRB.

Figure 2. Study Timeline.

Screening Phase		Intervention		Midpoint		Intervention			Post Intervention		
Assessments		Groups		Assessments		Groups			Assessments		
Labs	*Fxnl	Gent (n=12)	Saline (n=12)	None (n=12)	Labs	*Fxnl	Gent (n=12)	Saline (n=12)	None (n=12)	Labs	*Fxnl
UA Culture + Sensitivity	UDS US ~Intake forms	IC (n=6) 28.8 mg in 60 ml NS	IC (n=6) 60 ml NS	IC (n=6) No procedure	UA Culture + Sensitivity CBC CMP HCG	UDS US ~Intake forms	IC (n=6) 28.8 mg in 60 ml NS	IC (n=6) 60 ml NS	IC (n=6) No procedure SP (n=6) Catheter clamping for duration of instillation.	UA Culture + Sensitivity	UDS US ~Intake forms
CBC CMP HCG		SP (n=6) 28.8 mg in 60 ml NS	SP (n=6) 60 ml NS	SP (n=6) Catheter clamping for duration of instillation			SP (n=6) 28.8 mg in 60 ml NS	SP (n=6) 60 ml NS		CBC CMP HCG	
5 days		80 instillations - 7x/wk - 2x/d		5 days		80 instillations 7x/week – 2/d			5 days		

CBC, Complete Blood Count; CMP, Comprehensive Metabolic Panel; Gent, Gentamicin sulfate; IC, Intermittent Catheterization; Fxnl, Functional; HCG, Human Chorionic Gonadotropin (Pregnancy Test); NS, Normal Saline; SP, Suprapubic Catheter; UDS, Urodynamic Study; US, Ultrasound.

*The term "functional", abbreviated fxnl in this study, signifies an objective assessment of bladder functioning using urodynamic testing and ultrasound imaging.

IV. References

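### Staff contact differs by arm while symptomatic UTI is complaint-triggered, so both comparisons with no instillation are open to unequal ascertainment

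*Combined protocol and SAP*

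**What the plan says.** **Outcome.** Under Urine Sample Collection and Culture, "Symptomatic UTIs will be defined as a participant complaint of symptoms consistent with UTI", combined with urinalysis or microscopy findings and a culture threshold. No complaint means no episode.

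**Instillation arms.** Under Intravesical Gentamicin Sulfate Instillation, retention time is "incrementally increased by 15 minute intervals in the laboratory over the course of 3 - 4 weeks". The participant then goes home for one day, returns, goes home for three days, returns, and may then "begin the home intervention program of 6 days a week and 1 day in the lab". For saline, "participants will follow the same instillation training paradigm as mentioned above". Section II.B describes the laboratory phase differently: "blood pressure and heart rate will be continually monitored (approximately 1-2 weeks".

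**No-instillation arm.** For half the arm, Figure 2 reads "IC (n=6) No procedure". The other half, with suprapubic catheters, is trained in clamping in the laboratory. Once independent, "he/she will restart bladder clamping in the home setting, clamping the suprapubic catheter 4 times a day". No weekly laboratory day is stated for them after that.

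**Capture between visits.** Under Medical Event Reporting Unrelated to the Study, "All medical events for study participants will be recorded in a log for tracking and reporting, as the team is made aware of them". The International SCI Urinary Tract Infection data set is to be completed by researchers, but no completion interval is given. No symptom call, diary or query at a fixed interval is described for any arm.

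**The concern.** An outcome that begins with a complaint depends on the chance to complain and to give a qualifying urine sample. Someone attending daily for weeks and then weekly has many such chances. Someone at home with no procedure must take the initiative, and if treated elsewhere may never give a sample that meets the study definition.

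The Statistical Plan compares pre-to-post changes between arms, and between-group power is stated for gentamicin against no instillation. Episodes missed among controls after randomisation would look like improvement in that arm. Saline against no instillation is exposed too, and II.B relies on the control groups to ask whether existing colonisation is protective.

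**Working it through.** **1. The plan's power figure.** Inputs from the Statistical Plan: 12 per arm, mean reduction 2 against 0, SD 1.7 against 0, two-sided 0.05, unequal-variance t-test.

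- Standard error = 1.7/√12 = 0.491; noncentrality = 2/0.491 = 4.08; Welch degrees of freedom = 11.
- Power = 95.9%, against the stated 96%. The figure is reproduced. It assumes that a control change of zero is measured without error from ascertainment.

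**2. Contact days over 80 days.** The 80 days come from Screening and Enrollment. Figure 2's two blocks of 80 instillations at two a day give the same total (160/2 = 80). Laboratory days = build-up days + 1 (after one home day) + 1 (after three home days) + one for each full 7 days remaining. Daily attendance during the build-up and no interruptions are assumed.

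| Build-up | Day reached after second return | Full weeks left | Laboratory days |
|---|---|---|---|
| 1 week | 7+1+1+3+1 = 13 | 9 | 7+2+9 = 18 |
| 2 weeks | 20 | 8 | 14+2+8 = 24 |
| 3 weeks | 27 | 7 | 21+2+7 = 30 |
| 4 weeks | 34 | 6 | 28+2+6 = 36 |

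The full ladder from 30 to 120 minutes in 15-minute steps has 7 levels. At 3 stable days each, that is at least 21 days.

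For intermittent-catheter controls the documents state no contact outside the assessment blocks, which all arms share. For suprapubic controls they state initial training of unspecified length and nothing weekly afterwards. The imbalance is present under either build-up length.

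**3. Effect on an observed difference (illustration).** The documents give no detection rates, so all of these are assumptions: true means of 1.0 (control) and 0.5 (gentamicin), full detection under gentamicin, and detection p of 0.7 to 0.9 in affected controls.

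- Only the 6 intermittent-catheter controls affected: control mean = (6p + 6)/12 = 0.85 to 0.95. Difference = 0.35 to 0.45, or 70% to 90% of the true 0.5.
- All 12 controls affected: control mean = 0.7 to 0.9. Difference = 0.2 to 0.4, or 40% to 80% of the true 0.5.

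**4. Effect on power (illustration).** Assume 2 true UTIs per control in the counting period, an unaffected pre-treatment count, and under-detection only in the 6 intermittent-catheter controls. Spurious fall in the control mean = 2 × (1 − p) × 6/12.

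| p | Spurious fall | Apparent difference | Power, control SD 0 | Power, control SD 1.7 |
|---|---|---|---|---|
| 1.00 | 0 | 2.00 | 95.9% | 78.6% |
| 0.90 | 0.10 | 1.90 | 94.0% | 74.4% |
| 0.75 | 0.25 | 1.75 | 90.0% | 67.4% |
| 0.50 | 0.50 | 1.50 | 79.4% | 54.2% |

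Control SD 0 is the plan's assumption; 1.7 applies the gentamicin SD to both arms.

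**5. Direction.** Under-detection in controls lowers the post-treatment count in that arm alone. Gentamicin and saline would both look worse against no instillation, so the two contrasts move the same way. Over-reporting by controls would move both the opposite way.

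**The case against.** **Silence is not absence.** A reader might infer that controls have no contact at all. The documents do not say that. Screening and Enrollment promises a number of assessments during the protocol, section III.D leaves their frequency to the Research Medical Report, and the midpoint assessment is common to all arms. This stands in part: the supportable statement is that no contact schedule common to the arms is given. If one is intended, the repair is a matter of text.

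**The direction is not established.** A reader might infer that the imbalance must hide a benefit of gentamicin. The Blinding Plan treats the no-instillation assignment as known to everyone, so these controls might report more rather than less. This stands.

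**The supporting text is limited.** Under Bladder Assessments, infection symptoms are to be dealt with at once. A reader might take this as proof that contact drives detection, but it concerns care during and after assessments. The medical-event log likewise sits under events unrelated to the study. Neither defines how endpoint episodes are found. The point rests on the visit schedule, Figure 2 and the outcome definition.

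**The blinded comparison is intact.** Gentamicin and saline follow the same schedule. This stands and limits the scope.

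**Conclusion.** The point holds for comparisons of either instillation arm with no instillation. As written, the plan gives instillation participants roughly 18 to 36 laboratory days in 80. It states none between assessments for intermittent-catheter controls and no weekly day for suprapubic controls after training. The outcome depends on complaint and sampling, and nothing described equalises the opportunity for either.

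Net direction and size cannot be derived from the documents. The 40% to 80% range should not be read as the expected loss. It needs under-detection across the whole control arm, whereas 70% to 90% applies if only the intermittent-catheter half is affected. Both rest on assumed rates. Gentamicin versus saline is not called into question.

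This should be corrected: it touches the contrast used for between-group power, and the remedy changes no treatment.

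**What to change.** - **Common query.** Ask the same symptom questions at the same interval in all three arms, for example weekly, by phone or on the laboratory day. Use the International SCI Urinary Tract Infection data set already planned, and the same trigger for dipstick and culture.
- **Common counting rule.** Apply the protocol's symptomatic-UTI definition to every episode however it comes to light: by query, spontaneous complaint, assessment or outside provider. Record the route of detection so that episodes can be tabulated by route and arm.
- **Text.** Reconcile the two laboratory-phase lengths (section II.B and the gentamicin instillation procedure), and state what contact no-instillation participants have between assessments.

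Cost: 80/7 = 11.4, so about 11 short calls per control participant, plus a urine sample, and possibly a visit, when a query is positive. Instillation participants can be asked at visits they already make. A common query will not remove extra spontaneous reporting during daily attendance, or by unblinded controls, but the recorded route makes it visible.

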1. Blinding Plan: This is a double-blind study whereby the investigators, research assistants, research nurse and participants will be blinded as to the drug treatment designation. Once participants have been assessed for eligibility and enrolled in the study, they will be randomized into 1 of 3 different groups. Participants randomized to either group I or II will be blinded to the intervention fantibiotic instillation in group I or placebo (saline alone) in group II]. Gentamicin sulfate will be prescribed for the research participants by the study physician or nurse practitioner and instilled under the direction of the research nurse. Thus, the participants in groups I and II will not be able to discern their assigned treatment. To ensure the double-blind, only the study physician or nurse practitioner as well as the pharmacy, all of whom are not associated with the data collection or data analysis, will be un-blinded. Note, the research nurse assisting participants with the instillation will be blinded. All participants will be identified by number and the instillation solutions (gentamicin or placebo) will be numbered with the pharmacy having access to the code specifying which instillations are active and which are placebo for each participant. The investigators and direct research team members will not be permitted to have knowledge of the group assignments. In the case of a drug related adverse event, the study physicians will evaluate the event and prescribe treatment that will minimize or completely resolve the event if minor or moderate in severity and it does not interfere with activities of daily living or quality of life (as determined by the participant). Should it be determined that the event has gotten worse, or if the participant can no longer tolerate the event, the study drug will be discontinued, and the participant will be terminated from study participation. There are no expected reasons to unmask the study treatment. The study physician or nurse practitioner will decide if the blind is to be broken or not. The blind will not "routinely" be broken when a serious adverse event (SAE) occurs. If an SAE is probably or definitely drug-related, the drug/placebo intervention will be stopped, and the participant treated appropriately. Emergency drug code envelopes will be created by the pharmacy at the study site. These will be labeled by participant randomization number and contain information, which will un-blind the treatment of the individual subject. These envelopes are to be used only in extreme emergencies, such as when an emergency situation exists in which the participant's treatment would be affected by knowledge of his drug therapy, and there is no time to contact the Medical Monitor. Note, that at the end of the study, participants will be un-blinded to the intervention designation by the study physician or nurse practitioner. If a participant was randomized to the no instillation group, however, he/she may re-enroll into the study and directly receive the gentamicin intervention and are not required to wait until the end of study, as all parties are un-blinded and aware of the treatment (standard of care) in this instance. All data from participants re-enrolling into the gentamicin-only group will be kept separate from those who are enrolled in the main study who are blinded.

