Gentamicin sulfate will be prescribed for the research participants by the study physician or nurse practitioner. A formulation derived from 480 mg gentamicin sulfate diluted in 1 L normal saline will be used for instillation. The formulation will be prepared by the pharmacy, located at the study site (first floor of Jewish Hospital), in a laminar flow hood using USP 797 regulations just prior to the scheduled assessment (within 20-30 minutes) and stored in the refrigerator at a temperature range of 2-8°C until use in the outpatient setting. Gentamicin will be compounded for immediate use in single-dose, disposable BD 50ml Luer-Lok tip syringes. The container closure system for the diluted gentamicin sulfate solution is sterile and depyrogenated. A 60 ml syringe containing the gentamicin solution will be connected to the end of the catheter through which the solution will be slowly infused over 1-2 minutes (depending on bladder capacity – determined from initial Urodynamics) after drainage of urine is complete. The solution will remain in the participant's bladder for a least 30 minutes (unless the participant is experiencing autonomic dysreflexia, and in that case, immediately drained) with the goal of attaining 2 hours.

Participants will undergo initial instillations in the laboratory to determine the optimal bladder instillation storage time frame while monitoring blood pressure throughout the intervention. The initial intervention

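### Syringe sizes for gentamicin and saline are inconsistent, and the blinding plan does not say the two products come in matching syringes

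*Combined protocol and SAP*

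**What the plan says.** All references are to the combined protocol and SAP.

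- **Intravesical Gentamicin Sulfate Instillation (Research Procedures, item 1).** The solution is "A formulation derived from 480 mg gentamicin sulfate diluted in 1 L normal saline". On preparation: "Gentamicin will be compounded for immediate use in single-dose, disposable BD 50ml Luer-Lok tip syringes". On administration, two sentences later: "A 60 ml syringe containing the gentamicin solution will be connected to the end of the catheter". No transfer from one syringe to another is described.
- **Saline Instillation (item 2).** "A 50ml syringe containing saline will be connected to the end of the catheter". No fill volume is given.
- **Figure 2, Study Timeline.** The gentamicin entry is "28.8 mg in 60 ml NS" and the saline entry is also 60 ml, for both catheter types and both intervention periods.
- **Blinding Plan (II.B.1).** Masking works as follows: "the instillation solutions (gentamicin or placebo) will be numbered with the pharmacy having access to the code". The plan states that "the research nurse assisting participants with the instillation will be blinded", and that those unblinded are "only the study physician or nurse practitioner as well as the pharmacy". It does not address syringe model, fill volume or label format.

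**The concern.** A placebo is masked only if the people meant to be blind cannot tell it from the active product. A number on the syringe hides the contents but not the size of the barrel. If the gentamicin and saline instructions are each followed as written, one arm is treated from a 60 ml syringe and the other from a 50 ml syringe. The research nurse works with participants in both arms, so she could learn to recognise them.

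This matters because gentamicin versus saline is the only contrast that can be blinded. The no-instillation arm is openly known to everyone. A secondary issue is that the preparation text and the figure do not agree on the container for a drug dose.

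**Working it through.** **1. Reproduce the stated dose.**

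- Concentration, from item 1: 480 mg / 1000 ml = 0.48 mg/ml.
- Volume, from Figure 2: 60 ml.
- Dose: 0.48 × 60 = 28.8 mg.

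This equals the Figure 2 dose, so 60 ml is the volume consistent with the formulation.

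**2. Set the container statements side by side.**

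| Source | Gentamicin | Saline |
|---|---|---|
| Compounding sentence, item 1 | 50 ml syringe | not stated |
| Instillation sentences, items 1 and 2 | 60 ml syringe | 50 ml syringe |
| Figure 2 (instilled volume) | 60 ml | 60 ml |

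Two readings are open.

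- *The instillation sentences govern.* The arms use different syringes: 60 − 50 = 10 ml difference in nominal size.
- *The compounding sentence governs.* Both arms use 50 ml syringes and match, but the nominal size is 10 ml below the volume to be given.

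Figure 2 fixes the volume and not the container, so it does not settle which reading is right.

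**3. Participants concerned.** 12 gentamicin + 12 saline = 24 of 36.

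**4. Conditional illustration of dose.** The plan nowhere states a 50 ml fill. If a 50 ml syringe were filled only to its nominal size, the dose would be 0.48 × 50 = 24.0 mg. Relative to plan, 1 − 24.0/28.8 = 16.7% lower. This shows what the ambiguity could cost and is not a claim about what was given.

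**5. Who could be influenced.**

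- *Participants.* Each sees one syringe type, so size alone does not reveal the arm.
- *UTI definition (item 4).* It requires the participant's own complaint together with dipstick or microscopy and culture evidence, which limits what an unblinded nurse could change.
- *Clinician diagnosing UTIs that need systemic antibiotics.* The study physician or nurse practitioner is already unblinded by design.
- *Between-group power calculation (II.B.2).* It uses gentamicin versus no instillation, where allocation is open anyway.
- *Remaining routes.* Researchers complete the UTI data set (item 8), and a research urology nurse conducts the urodynamic tests (III.E, Bladder Assessments). The protocol does not say whether either task falls to the nurse who assists with instillations.

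**The case against.** The best defence is that the plan already settles what matters. Figure 2 is the only place that states an instilled volume, it gives 60 ml in both arms, and it agrees with the formulation. Items 1 and 2 name syringe sizes, not fills, and a nominal size is not a usable capacity: the documents do not say what the 50 ml syringe can hold. The compounding sentence is the most specific description of the pharmacy product, and it matches the saline syringe. The mention of 60 ml at instillation may be loose wording for the volume. The Blinding Plan also has real substance: numbered product, a code held by the pharmacy, named unblinded roles and emergency envelopes.

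Much of this stands. Dose and volume are not in conflict, no underdosing is shown, and different syringes were probably never intended. The objection does not say which syringe sentence governs. The matching-syringe reading works only by setting aside an explicit administration instruction. These sections are what the pharmacy and nurse would work from, and the Blinding Plan has no statement on the container to fall back on.

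**Conclusion.** The concern holds as a minor fault. The syringe text contradicts itself within the gentamicin section, differs between the two arms' instillation instructions, and is not rescued by any statement that the products match. On one of the two available readings, a nurse declared blind would see an arm-specific syringe, in the contrast covering 24 of 36 participants.

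The text mismatch is certain. An effect on the blind is only possible: it assumes that the instillation sentences are followed literally and that the nurse has some part in recording or measuring outcomes, which the protocol leaves open. The documents do not support an estimate of bias, and none is offered. The 28.8 mg dose is sound; the 24.0 mg figure applies only under a fill that the plan does not state.

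**What to change.** Three wording changes are needed.

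- **Item 1 (gentamicin).** Name one syringe model that holds 60 ml, filled with 60 ml (28.8 mg), and use it in both the compounding and the instillation sentences.
- **Item 2 (saline).** Specify 60 ml of saline in that same syringe model.
- **Blinding Plan (II.B.1).** Add: *The pharmacy will supply gentamicin and saline in the same syringe model, fill volume and label format, identified only by number.*

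The cost is an edit to two procedure sections and one added sentence. Sample size, visits and analysis stay as they are, and Figure 2 needs no change.
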